The first five participants will be enrolled into an open label pilot study, in which they will automatically receive the HEROIC intervention. The participants will be interviewed after program completion to get feedback on the data collection instruments, intervention content including the number of visits and user-friendliness of intervention components (e.g., purpose in life activity), and satisfaction with the overall program process. These interviews will be conducted over phone, zoom, or in-person. This feedback will be used to modify the HEROIC intervention for the waitlist control trial that will begin enrollment following the open label phase.

Randomization:

Caregivers will be randomized using REDCap to receive either: (1) intervention or (2) waitlist. Random assignment will be stratified by spousal vs non-spousal caregivers due to evidence of increased caregiver

[figure not shown]
burden among non-spousal caregivers. Within 48 hours of the baseline data collection visit, we will randomize using REDCap randomization and communicate the assignment to participants by letter. Waitlisted Control Group: The waitlisted group will receive usual care for caregivers for the first 12 weeks, which is normally limited to inclusion in some clinical assessment, teaching during patient visits and informational handouts. Waitlisted participants will receive monthly study postcards to encourage retention. After 12 weeks, they will begin the intervention. The 24-week assessment will measure improvement following the intervention for waitlisted participants.

Immediate Intervention Group: We will inform the nurse interventionist of the new participant. The intervention nurse will contact the participant within one week to schedule the first appointment. After 12 weeks, immediate intervention group participants will do a post-intervention assessment. The 24-week assessment will measure whether immediate intervention participants continue the strategies on their own and whether they continue to improve on the self-report scales.

Intervention Delivery Characteristics:

The intervention will consist of an assessment-driven, tailored package of interventions delivered by a

Figure 2. Group assignment and outcome measurement

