nurse interventionist. We propose an intervention incorporating 5 individualized, nurse-led, homebased or virtual (phone, HIPAA compliant Zoom or DoxyMe video call) sessions, with telephone check-ins and text reminders, according to participant preference. We have based the timing of study visits on previous experiences of the mentorship team and similar studies with this population, however we will use the open-label pilot interview feedback to provide feedback for further refinement of timing visits. ^{41–43} The intervention will be guided by the theory and evidence-based practices that have been successful

in previous work (Table 1).^{31,41} Every participant will receive each component of the intervention but interventionists will tailor content to each participant's goals.

Nurse interventionists will be trained and equipped with education materials vetted by national organizations leading preventive health research such as the American Heart Association (Healthy for Good⁴⁴) and National Institute of Aging (Go4Life⁴⁵) for each broad category of preventive health behaviors (nutrition, physical activity, stress management, sleep and healthcare utilization).

As part of the intervention, the nurse and caregiver will prioritize the health category that they would most like to address and then set goals. Allowing the caregiver maximum control over this goal setting, without placing additional burden on the caregiver is one aspect of increasing self-efficacy and person-centeredness. Because the intervention will allow participants to pick their own health goals, we will measure goal attainment related to health behaviors, rather than a standardized survey of predetermined preventive health behaviors.

Table 1: Intervention Components and evidence basis for component selection

| Intervention Component | Evidence Basis for Component |
|--|--|
| 1) Whole-person assessment including physical, psychosocial, | - Caregiver physical and psychosocial assessment is suggested by HF guidelines, but not commonly used in practice ^{17,46–48} |
| preventive health behaviors and challenges in caregiving | - Involving the caregiver in assessment and encouraging them to set their own goals is person-centered, builds rapport and increases participation. 41,49,50 |

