| Week 10 | Discuss how caregiver will involve social support in next goals |
| | Walking meeting (if virtual: suggest participant take a walk during call) |
| Phone Check-in | Review/edit purpose statement |
| Week 12 | Assess goal attainment and strategies to achieve goal |
| | Walking meeting (suggest participant take a walk during call) |
| Data Collection Visit | Heartrate Variability Measurement |
| Week 12 | Survey |
| Data Collection Visit | Heartrate Variability Measurement |

Week 24 Survey

Death of the Patient: If the patient/care recipient of the enrolled caregiver/study participant dies during the study, we will send a sympathy card. In that communication, we will ask the caregiver if they would like to participate a modified version of the intervention for bereavement: 1-3 visits (scheduled every other week) with a nurse for bereavement support within two months of the death of the care recipient. Additional instrumental support resources will be suggested such as grief support groups, referral to Roberta's House and bereavement resources for tasks to complete after someone you love dies. If the caregiver chooses to discontinue their participation, we will discontinue study contact and data collection. Data from caregivers whose care recipient dies will be excluded from analysis of primary and secondary outcomes.

Research Variables and Measurement

We chose measures (Table 2) based on previous RCT experience of mentors as well as those that met the following criteria: 1) possess known reliability and validity with ethnically diverse samples; 2) are sensitive to change from an intervention; 3) have clinical relevance; 4) Common Data Elements to connect this work with the broader literature and 5) represent objective as well as subjective indicators of the domains we seek to impact. Finally, we sought to achieve a balance between psychometric quality and practical considerations such as respondent burden. All instruments with the exception of demographics will be measured at baseline, 12 and 24 weeks. Patient characteristics will be obtained from chart review.

^{*} Waitlist control group will begin intervention at week 12.

Table 4: Constructs, Instruments and Reliability

| Theoretical Construct | Instruments and variables | Cronbach's alpha | | | |
|--|--|---------------------|--|--|--|
| | Contextual Factors | | | | |
| | 1)How well does the amount of money you have take care | | | | |

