| Financial Strain | of your needs? 2)In general, how do your finances usually | - | | | |
| | work out at the end of the month? | | | | |
| Social Support | ENRICHED Social Support Instrument ⁶⁹ | 0.88 | | | |
| | Caregiver Characteristics | | | | |
| Demographics | Age, Race, Gender | - | | | |
| Depression | Patient Health Questionnaire (PHQ-8) ⁷⁰ | 0.86 | | | |
| Perceived Stress | Perceived Stress Scale ⁷¹ | 0.82 | | | |
| Co-morbidities | Charlson Comorbidity Index ^{72,73} | 0.81 | | | |
| | Patient Characteristics | | | | |
| Functional Status | New York Heart Association Class (chart review) | - | | | |
| Cognition | Mini-mental status exam (chart review) | - | | | |
| Co-morbidities | Charlson Comorbidity Index (chart review) ^{72,73} | 0.81 | | | |
| | Katz independence in activities of daily living ⁷⁴ (caregiver | | | | |
| Independence of Care | report) | 0.84 | | | |
| Recipient | Lawton instrumental activities of daily living ⁷⁵ (caregiver | 0.85 | | | |
| | report) | | | | |
| | Potential Mechanisms | | | | |
| Self-efficacy | Coping self-efficacy ⁷⁶ | 0.91 | | | |
| Resilience | Heart rate variability | - | | | |
| | Caregiver Outcomes | | | | |
| Goal Attainment: Preventive Health Behaviors | Goal Attainment Scaling ⁷⁷ | 0.91 | | | |
| C . D 1 | Oberst Caregiver Burden Scale ⁷⁸ | 0.00 | | | |
| Caregiver Burden | 2 domains: time caregiving and task difficulty | 0.90 | | | |
| | Modified Caregiver Strain Index ^{79,80} | 0.86 | | | |
| Quality of Life | NeuroQOL | 0.85 | | | |
| Quality of Life | RAND 36-Item Short Form Survey | | | | |
| | 1) "Since our last contact, were you seen at an emergency | | | | |
| Health care utilization | room or a medical facility (e.g., Urgent care) for outpatient | | | | |
| | treatment?" | - | | | |
| | 2) "Since our last contact, were you hospitalized, or did | | | | |
| | you stay in a hospital observation unit for any reason?"* | | | | |
| Fatigue | PROMIS Fatigue – Short Form | | | | |
| Family Function | Family Assessment Device - Global/General Functioning | | | | |
| | Scale | | | | |

^{*}adapted from the Atherosclerosis Risk in Communities (ARIC) study annual follow-up questionnaire for healthcare utilization

Data collection and management:

Data Collection:

1) Questionnaires - Baseline, 12 and 24-week data will be collected by research assistants masked to treatment assignment. All data will be entered into RedCap.⁸¹

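### The two health-care utilisation items use an undefined recall anchor, so the look-back period can differ by arm and is unclear at baseline

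*Combined protocol and SAP*

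**What the plan says.** Table 4 in Section 4 (Research Variables and Measurement) lists health care utilization under Caregiver Outcomes, with two yes/no items. The first, on emergency or outpatient treatment, begins "Since our last contact, were you seen at an emergency". The second, on hospital or observation stays, begins "Since our last contact, were you hospitalized, or did". The table footnote says the items were "adapted from the Atherosclerosis Risk in Communities (ARIC) study annual follow-up questionnaire for healthcare utilization". Neither the table nor the text defines a contact or gives a look-back in weeks.

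On timing, the same section states: "All instruments with the exception of demographics will be measured at baseline, 12 and 24 weeks".

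Contact differs by arm. Table 3 gives the immediate arm nurse visits or check-ins at weeks 1, 3, 4, 6, 8, 10 and 12, and Intervention Delivery Characteristics describes the sessions as coming "with telephone check-ins and text reminders, according to participant preference". For the other arm, the Randomization text says: "Waitlisted participants will receive monthly study postcards to encourage retention". The footnote to Table 3 has the waitlist arm starting the intervention at week 12.

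**The concern.** A question that asks about events since a contact measures events over whatever time has passed since that contact. If that time depends on allocation, two arms with the same event rate will give different percentages. Masking the assessor does not help, because the difference comes from exposure time and not from how answers are recorded. It also cannot be repaired later: a yes/no answer does not reveal which contact the participant had in mind.

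At stake is a listed caregiver outcome in a pilot whose purpose is to gauge initial effect sizes. Percentages by arm could show a difference, or hide one, purely because of the contact schedule.

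**Working it through.** The plan gives no recall window and no utilisation rate, so there is no figure of its own to reproduce.

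**Step 1: length of the look-back.** Window = survey week minus week of the last contact. Contact weeks come from Table 3. For the waitlist arm after week 12, I assume the same schedule shifted by 12 weeks, so its last contacts fall at about weeks 22 and 24.

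| What counts as a contact | Week 12, immediate | Week 12, waitlist | Week 24, immediate | Week 24, waitlist |
|---|---|---|---|---|
| Previous study assessment | 12 | 12 | 12 | 12 |
| Nurse contacts, not postcards | 12 − 12 = 0, or 12 − 10 = 2 | about 12 | 24 − 12 = 12 | 24 − 24 = 0, or 24 − 22 = 2 |
| Nurse contacts and postcards | 0 to 2 | about 4 or less | 12 | 0 to 2 |

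The value of 0 applies if the week-12 telephone check-in takes place. The paragraph on study duration makes calls between visits a matter of participant preference; without that call the gap is 2 weeks.

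**Step 2: effect on reported percentages.** Assume no treatment effect, a constant hazard, and a 12-week probability p of any event. Then P(yes over w weeks) = 1 − (1 − p)^(w/12). The value of p is my assumption. With p = 15%:

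- w = 1: 1 − 0.85^(1/12) = 1.3%
- w = 2: 1 − 0.85^(2/12) = 2.7%
- w = 4: 1 − 0.85^(4/12) = 5.3%
- w = 12: 15%

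With 22 per arm, 2 weeks against 12 weeks means 22 × 0.027 = 0.6 expected reporters against 22 × 0.15 = 3.3. If postcards count, it is 0.6 against 22 × 0.053 = 1.2.

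**Step 3: sensitivity to the assumed rate.** For p = 10% and 25%, the 2-week figures are 1.7% and 4.7%. For p from 5% to 30%, the artefactual risk ratio for 2 against 12 weeks stays between 0.17 and 0.19. For 2 against 4 weeks it is about 0.50. The ratio depends on the windows and hardly at all on the rate.

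**Step 4: baseline.** The Recruitment text schedules the baseline visit within 10 days of e-consent. The look-back may therefore be 10 days or less, or 10/84 of a 12-week period. With p = 15%, 1 − 0.85^(10/84) = 1.9%. A participant group with a constant rate could go from 1.9% at baseline to 15% over a 12-week window. Both arms share this at baseline, so it does not separate them, but within-arm change would have no meaning. Reading the anchor as the previous assessment does not help here, because there is no previous assessment.

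**The case against.** The strongest reply is that research assistants unaware of allocation collect the survey, not the nurse. When an assistant asks about our last contact, the natural meaning is the previous assessment, and the windows are then 12 against 12 weeks at both follow-ups. That reading is reasonable, but the plan does not secure it. The Data Collection text lets surveys go out by email through REDCap, where no assistant is present and the words can equally mean the whole study team, nurse included. Where an assistant does ask, sorting out which contact is meant could reveal allocation, which the Blinding paragraph asks participants not to discuss.

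A second reply is that if every staff contact counts, arranging the follow-up visit counts too, and both windows shrink towards zero. This is also possible. It adds another reading and does not remove the problem.

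A third reply stands in full: the analysis plan compares no utilisation data between arms by model. In Section 7 the GEE models name QOL as primary and self-efficacy and HRV as secondary; utilisation falls only under the general statement on descriptive analysis.

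A reader might infer that the wording biases the trial in favour of the intervention. The documents do not support that. The bias depends on the reading, and its direction reverses between weeks 12 and 24. Nor does the plan say that fewer events are better for the first item: Intervention Delivery Characteristics lists healthcare utilization among the preventive health behaviors. It would also go too far to say what the anchor meant in the source questionnaire. The footnote says only that it was an annual follow-up.

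**Conclusion.** The point holds as an undefined recall anchor combined with contact schedules that differ by arm. Bias is possible, not demonstrated. If nurse contacts count, identical arms would appear to differ at week 12 by a risk ratio of about 0.17 to 0.19, or about 0.50 if postcards count, with the reverse pattern at week 24. If participants answer from the previous assessment, the follow-up comparison is sound and only the baseline problem remains.

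These sizes rest on a constant hazard, no true effect, a 2-week window in the immediate arm, and assumed 12-week risks of 5% to 30%. The counts are small, a few participants per arm in a descriptive table. The primary outcome and the named secondary outcomes are untouched. The point still deserves correction before data are collected, because the information lost cannot be recovered and the remedy is cheap.

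**What to change.** Replace the opening of both items with a dated window that is the same in both arms:

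- at baseline: *In the past 12 weeks, …*
- at weeks 12 and 24: *Since your last study survey on [date], …*

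Have REDCap pre-fill the date from the previous completed survey. The window is then about 12 weeks in each arm at every assessment, whoever asks the question and however it is sent, and the artefactual risk ratio is 1.0. The stored date also shows any window that is longer because a survey was late or missed.

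The cost is the rewording of two items, one pre-filled field and a minor amendment. The downside is a small further departure from the source wording, which has already been adapted.

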The proposed study is significant because we will test an intervention to improve health behaviors, caregiver burden and QOL among caregivers who are at risk for negative health outcomes and who receive little attention in our current healthcare system. Further, this study will test the HEROIC intervention in an ethnically diverse, predominantly low-income population with a large number of non-spousal caregivers.

We have completed 2 mixed methods studies with advanced HF caregivers. The first, with caregivers of advanced HF patients living with a left ventricular assist device and the second, was phase 1 of our P30 pilot study and enrolled recently hospitalized advanced HF patients and their caregivers. We have learned that caregivers are adapting their homes and lifestyles to accommodate HF monitoring, work and worry and that caregivers often lose track of their own needs in the midst of crisis caregiving for advanced HF patients. We have also developed the Caregiver-Support intervention, which has been approved by the IRB and is ongoing, which includes 2 of the intervention components that will also be tested in the proposed HEROIC study – the whole person assessment and purpose in life activities. However, the P30 intervention is focused on instrumental and social support. Thus, this pilot will build from the previous work and add an important focus on preventive health behaviors.

[figure not shown]
Investigators

Our research team has worked together on studies in various combinations for years and represents nationally and internationally known investigators with expertise in the proposed methods. The PI is a

junior investigator ([name]) with extensive clinical and research experience with heart failure patients and caregivers. As a junior investigator, she will be mentored by Drs. [name], [name]. [name] has fielded multiple community trials that involve nurse-led home visits and goal setting.^{7,8} [name] is an expert in mental health and mixed methodology. Dean [name] is a global leader in HF and has an established program of research improving cardiovascular care and caregiving.

Conceptual Framework

Figure 1: Conceptual Framework for Heart Failure Resilience Intervention for Caregivers (HEROIC)

[figure not shown]

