acceptable through the use of human-centered design, involving end users in development and testing of the intervention. We will use mixed methods to evaluate the open label phase and the pilot RCT. The proposed development aim and mixed methods allow for triangulation of multiple forms of data to inform development, feasibility and acceptability (Table 1).

Recruitment:

Recruitment of caregivers of patients with HF treated in the Johns Hopkins Health System.

Target population: The recruitment sites provide early post-hospitalization guideline-directed HF follow-up care. The clinics serve primarily low-income older adults. Inclusion: Caregivers of patients served by these settings will be included if a) the patient was hospitalized within 6 months b) they agree to work on goals that address health behaviors and/or decrease burden c) caregivers live with the patient or visit them to provide care more than 3 times per week d) the caregiver is 50 years or older. Exclusions: Caregivers who themselves have a terminal diagnosis or are cognitively impaired (as determined by 6-item screener) will be excluded as goal setting and response to the intervention may vary in these groups. Caregivers who consented to IRB00203584 and participated in at least one intervention visit.

Method 1: Once we are notified of potentially interested participants through clinic referral, we will screen the caregiver for eligibility by a RedCap survey, phone, zoom, or in person in clinic. Method 2: We will distribute a recruitment flyer in the waiting rooms of the recruitment sites. Once we are notified of potentially interested participants through self-referral though the recruitment flyer, we will screen the caregiver for eligibility by a RedCap survey, phone, zoom, or in person in clinic.

If the caregiver is eligible and interested in participating, then e-consent will be obtained (by phone, HIPAA compliant Zoom or DoxyMe video call) regardless of recruitment method. We will schedule the caregiver's baseline data collection visit within 10 days of e-consent.

Open Label Phase:

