fidelity through records of home sessions (by date and duration), checklists completed by study team members and direct observations and discussions concerning intervention engagement to evaluate receipt, and enactment. Ten percent of sessions will be audio taped which will be reviewed by the research coordinator using a priori monitoring checklists developed for this trial. All data collection and intervention interactions will be recorded. Evaluation will include periodic assessments of data quality, participant recruitment, accrual, and retention. Feedback will be provided to each interventionist who will provide case presentations in supervisory sessions. Bi-weekly meetings of the nurse interventionist with the Research Coordinator, the PI, and [name] will assure on-going fidelity to the intervention.

Study duration and number of study visits required of research participants: Participation in the study will consist of initial study consent, baseline, 12 and 24-week data collection and 5 study interactions for the intervention. Based on participant preference, the nurse interventionist may also arrange phone calls between visits to assess progress towards goals.

Blinding, including justification for blinding:

Research staff performing outcome assessments will be masked to assignment. Prior to follow-up assessment, staff will use standardized language to instruct participants not to discuss their treatment allocation with staff.

Justification of why participants will not receive routine care or will have current therapy stopped: n/a

Justification for inclusion of a placebo or non-treatment group: Both groups will receive the intervention. We are using a waitlist design to have a comparison to usual care.

Definition of treatment failure or participant removal criteria: n/a

Description of what happens to participants receiving therapy when study ends or if a participant's participation in the study ends prematurely: n/a

5. Inclusion/Exclusion Criteria

Screening:

1) Six-Item Screener; Callahan CM et al., 2003

To be eligible for inclusion caregivers must:

- 1) 50 years or older and
- 2) English speaking
- 3) Live with the heart failure patient or visit the patient at least 3 days per week to provide care or support.
- 4) Provide support to the patient for at least 1 Instrumental Activity of Daily Living
- 5) Care for a heart failure patient hospitalized in the last 6 months

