- 6) Live within a 1.5 hour driving radius of the Johns Hopkins Hospital

Exclusion Criteria:

- 1) Caregivers with cognitive impairment using the six-item screener will be excluded. Severe Cognitive Impairment would make active participation in interviews and survey completion very difficult.
- 2) Non-English speakers will be excluded. Non-English speakers may have unknown needs that cannot be addressed with this intervention.
- 3) Caregivers with terminal diagnosis will be excluded as goal setting at end of life may be different than without a terminal diagnosis.

4) Caregivers who consented to IRB00203584 and participated in at least one intervention visit. These participants have received components of the intervention.

6. Drugs/ Substances/ Devices

N/A

7. Study Statistics

Exploratory and descriptive analysis will be completed for all study variables. Variables will be examined for normality and examined with means and standard deviations or medians and interquartile ranges accordingly. Baseline characteristics comparing the two groups (waitlist vs. immediate intervention) will be assessed. Any differences between the groups will be adjusted for further analysis. The significance level will be set at 0.05. Sensitivity analyses will be conducted adjusting for variables on which the group differ and compared to the pattern of results in the main analyses.

Analysis Plan:

Qualitative Analysis (Aims 1 and 3) - A qualitative descriptive analysis approach will be applied to data analysis of semi-structured interviews. 82,83 The codebook will be adjusted as needed. Similar codes will then be grouped into categories/themes that express the latent idea of grouped codes which will be used to refine the intervention protocol.

Aim 1 – In addition to qualitative analysis, descriptive analysis will be used to examine all quantitative data. Joint displays will be used to provide a structure to discuss the integrated quantitative and qualitative analysis and assist the study team in making changes to intervention components and overall protocol to improve feasibility and acceptability.⁸⁴

Aim 2 -

a. Primary outcome variable.

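### Exclusion 4 screens out past visits under IRB00203584 but not pending ones, and nothing bars or records such visits during HEROIC follow-up

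*Combined protocol and SAP*

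**What the plan says.** The exclusion appears twice in the combined protocol and SAP. Under Recruitment in Section 4 it reads "Caregivers who consented to IRB00203584 and participated in at least one intervention visit", with no reason given. Exclusion criterion 4 in Section 5 repeats it and adds the reason: "Caregivers who consented to IRB00203584 and participated in at least one intervention visit. These participants have received components of the intervention".

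Section 3 (Background) describes related work by the same team: "We have also developed the Caregiver-Support intervention, which has been approved by the IRB and is ongoing". It says that this intervention "includes 2 of the intervention components that will also be tested in the proposed HEROIC study – the whole person assessment and purpose in life activities", and continues: "However, the P30 intervention is focused on instrumental and social support". Instrumental support and social support are components 5 and 6 of HEROIC in Table 1.

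Under Randomization in Section 4, the waitlist arm has usual care for 12 weeks and then starts HEROIC. The sample size text in Section 7 presents the waitlist as an untreated comparison and makes an initial effect size against usual care the aim of the randomised phase. The Section 7 models compare change between arms to 12 weeks and also to 24 weeks.

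**The concern.** The reason given for exclusion 4 is exposure to HEROIC components outside HEROIC. That reason applies as much to exposure after randomisation as to exposure before it, but the rule looks only backwards. A caregiver with visits under IRB00203584 still to come passes screening and could have them during follow-up.

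In the waitlist arm, visits in weeks 0-12 would mean that some controls are not on usual care, in the only period when the trial has an untreated comparison. In the immediate arm, the same visits would be a co-intervention whose benefit is credited to HEROIC. Between weeks 12 and 24 they could affect the waitlist arm's measured response to HEROIC and the immediate arm's maintenance assessment. Because no planned measure captures such visits, the team could not tell afterwards whether any of this had happened.

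**Working it through.** The plan gives no figure on this point, so there is nothing to reproduce. The check is mainly one of text, followed by an illustration of size.

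**Text**

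1. *Who is excluded.* Both statements join two conditions, consent to IRB00203584 and at least one visit. Someone who consented but has had no visit meets only the first and stays eligible.
2. *What happens after randomisation.* I found no bar on visits under IRB00203584, no requirement to leave that study, and no rule for handling such visits in the analysis. Section 4 gives participant removal criteria as not applicable.
3. *Whether exposure would be seen.* The health care utilization items in Table 4 cover emergency or outpatient facility care and hospital stays. The fidelity records cover HEROIC's own sessions. Neither would pick up visits under another protocol.
4. *Overlap of content, if IRB00203584 is Caregiver-Support.* Two components are named as shared. The instrumental and social support focus matches two more by name. That is up to 4 of the 6 components in Table 1.
5. *Overlap of population.* HEROIC requires "Care for a heart failure patient hospitalized in the last 6 months". The similar population in Section 3 belongs to an earlier study, which "was phase 1 of our P30 pilot study and enrolled recently hospitalized advanced HF patients and their caregivers". That study is listed as completed. Section 3 gives no eligibility criteria for Caregiver-Support.

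**Size (illustration only)**

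From Section 7: 22 per arm. Assumed, because the document does not give them: the true standardised effect d, the number c of waitlist caregivers exposed, and the fraction f of HEROIC's effect that each of them receives.

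With waitlist exposure only, the diluted effect is d × (1 − f × c/22). For d = 0.50:

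| c | f | Calculation | Diluted effect | Relative loss |
|---|---|---|---|---|
| 1 | 0.5 | 0.50 × (1 − 0.5/22) | 0.49 | 2.3% |
| 2 | 1/3 | 0.50 × (1 − 0.667/22) | 0.485 | 3.0% |
| 2 | 0.5 | 0.50 × (1 − 1/22) | 0.48 | 4.5% |
| 4 | 0.5 | 0.50 × (1 − 2/22) | 0.45 | 9.1% |
| 4 | 4/6 | 0.50 × (1 − 2.667/22) | 0.44 | 12.1% |
| 4 | 1 | 0.50 × (1 − 4/22) | 0.41 | 18.2% |
| 6 | 1 | 0.50 × (1 − 6/22) | 0.36 | 27.3% |

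The standard error of Hedges' g at 22 per arm and g = 0.50 is √(2/22 + 0.50²/88) = √(0.0909 + 0.0028) = 0.31. The 95% interval is 0.50 ± 1.96 × 0.306, or about −0.10 to 1.10. The loss at c = 4 and f = 0.5 is 0.045, about 0.15 standard errors. The last row, an extreme case, loses 0.136, about 0.45 standard errors.

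**Both arms exposed**

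Let c′ immediate-arm caregivers each gain an extra fraction h of the effect. The contrast becomes d × (1 − f × c/22 + h × c′/22). It falls if f × c exceeds h × c′, rises if the reverse holds, and is unchanged if they are equal. The document fixes none of these four quantities.

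**The case against.** The best defence is that the wording does what it was written to do. It removes caregivers who have already received components and keeps those who signed a consent form but received nothing, such as people who withdrew before any visit. Excluding everyone who ever consented would lose suitable caregivers for no gain. This stands, and the fix should leave that group eligible.

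Several further objections also hold. No sentence identifies IRB00203584 as Caregiver-Support; that is an inference, though a strong one, because the reason attached to the exclusion fits the Section 3 description of shared components. The word ongoing could refer to remaining visits, follow-up or analysis, and does not establish that the study is still recruiting. The consent pages were not available for this review, so a co-enrolment condition there would not have been seen.

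A reader might infer that the two studies recruit the same caregivers at the same time, so that contamination is to be expected. The document does not support this. The recently hospitalised population is attributed to the completed first phase of the P30 pilot, not to Caregiver-Support, and no number of consented but unvisited caregivers is given. A reader might also infer that the 12-week effect will be materially understated. That would require c, f and no offsetting exposure in the immediate arm to be known. A count of shared components is not a share of effect, and f near 1 sits poorly with Section 3, which presents preventive health behaviors as HEROIC's addition.

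These objections limit the likelihood and size of the problem. They do not close the gap in the rule.

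**Conclusion.** The gap is real as a matter of text. Followed as written, exclusion 4 admits a caregiver with visits under IRB00203584 still to come, and nothing later in the plan prevents or records those visits. This runs against the rule's own stated reason. Its importance depends on IRB00203584 being the Caregiver-Support study, which the team can confirm at once.

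The size cannot be derived from the document. Under the assumed values above, a handful of exposed controls would shift the estimate by well under one standard error, and exposure in both arms leaves even the direction open. If only controls are exposed, the dilution is a bias that the confidence interval does not reflect, so small size is not a reason to ignore it when prevention is this cheap. The point is of low-to-moderate priority. It does not undermine the design.

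**What to change.** 1. In Section 4 (Recruitment) and in Section 5, extend exclusion 4 to caregivers currently enrolled in IRB00203584 with intervention visits still pending. State that those who consented but withdrew, or who will receive no visits, remain eligible. Say which study IRB00203584 is.
2. State that participants in both arms do not start intervention visits under IRB00203584 until their HEROIC 24-week assessment is complete. The limit should be the same in each arm: weeks 12-24 are when the waitlist arm's response to HEROIC is measured, and the Section 7 models still compare the arms at 24 weeks.
3. At the 12- and 24-week assessments, record any visits received under IRB00203584. Keep all participants as randomised in the main analysis, and add a sensitivity analysis omitting those exposed. It belongs with the supplementary analyses that Section 7 already foresees for post-randomisation data, because omission after randomisation can itself unbalance the arms.

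The cost is a short amendment in two places, a question at two existing assessments, and a check of enrolment and visit status at screening. Applying the present rule already requires knowing consent and visit history under IRB00203584, so the added information is whether visits remain. A few otherwise eligible caregivers may be lost or deferred. The schedule of IRB00203584 is not in the document, so the team should confirm that item 2 is workable under that protocol. If it is not, item 3 is the minimum.
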